Clinical outcomes of intravenous vitamin C synergy with Tyrosine kinase inhibitor in lung adenocarcinoma patients with epidermal growth factor receptor mutations

November 14, 2018

Study Protocol and Statistical Analysis Plan

Background:

Vitamin C (VitC) infusion are widely used by integrative and complementary cancer practitioners for many years. In the last 10 years, many studies have shown that pharmacological concentrations of VitC can selectively kill tumor cells. A series of in vitro experiments [1], animal experiments [2-4] and Phase I-II clinical trials [5-7] have successively confirmed that VitC at pharmacological concentrations has the effect of inhibiting the growth of various tumors, including lung cancer.

Our Phase I clinical study, "The safety and pharmacokinetics of high dose intravenous ascorbic acid synergy with modulated electrohyperthermia in Chinese patients with stage III -IV non-small cell lung cancer", confirmed the safety of high-dose vitamin C in combination with deep hyperthermia in advanced non-small cell lung cancer, the concentration is as high as 1.5g/kg.d, 3 times a week. There were no significant adverse reactions. And it can significantly improve the quality of life (QoL). Our Phase II clinical trial in 2018 confirmed that IVC + mEHT treatment can significantly improve QoL, prolonge progression free survival (PFS) and overall survival (OS), and moderate cancer-related inflammation in advanced NSCLC patients. The article is already in the submission stage.

Recently we noticed that patients with epidermal growth factor receptor (EGFR) mutation who were taking tyrosine kinase inhibitor (TKI) with intravenous VitC every week had a relatively longer drug resistance time in our oncology center. We believe that it is necessary to observe whether intravenous VitC simultaneously with TKI can prolong the time of drug resistance in patients with EGFR mutations.

Objectives:

The purpose of this study was to investigate the effect of intravenous VitC in combination with TKI on the tumor size, QoL, PFS and OS in lung adenocarcinoma patients with EGFR mutation

Inclusion Criteria:

- Primary non-small cell lung cancer (adenocarcinoma) with EGFR mutations on exons 19 and 21.
- 18 years old to 75 years old.
- During the trial, patients were prescribed TKI (received initial treatment within 2 months, or change medication within 2 months) and did not receive chemotherapy or radiotherapy at the same time.

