- Eastern Cooperative Oncology Group(ECOG) performance status are 0 to 2.
- Expected survival over 3 months.
- Household registration is Guangdong Province.

Exclusion Criteria:

- Co-morbid conditions that affect survival: end stage congestive heart failure, unstable angina, myocardial infarction (within the past 6 weeks), and uncontrolled blood sugars of greater than 300 mg/dL, known chronic active hepatitis or cirrhosis.
- Glucose-6-phosphate dehydrogenase deficiency (G6PD) (a relative contraindication).

- Patients who are allergic to VitC.
- Patients with HIV and other infectious diseases.
- Patients who are taking anticoagulants and have coagulopathy;
- Combine dysfunction of important organs such as heart, lung, liver and kidney;
- Patients with impaired renal function (serum creatinine content > 1.2 mg/dL)
- Compromised liver function with evidence of Serum total bilirubin content, ALT and AST > 2 times normal reference value.
- Pregnant or lactating female.
- Smoking and alcohol abuse patients;
- Anti-infective treatment is required for systemic or localized serious infections;
- Patients with hyperuric acidosis (normal: 91-456 $\mu\text{mol} / 24\text{h}$ (8-40mg / 24h));
- Wilson's disease.
- Evidence of significant psychiatric disorder by history or examination that would prevent completion of the study or preclude informed consent.
- Any condition that impairs the patients' ability to swallow, which impairs drug absorption or drug kinetic parameters, including any kind of gastrointestinal resection or surgery;
- History of surgery of visceral organs within 6 weeks before the trial.

Study design:

Experimental period: 12.05.2018~31.12.2019

Method:

In experimental group:75 patients received a weekly intravenous Vitamin C injection (dose: 30 g / time, once a week, treatment termination when the disease progress is confirmed) in combination with daily TKI; In the control group:75 patients received only TKI daily. (dose: Osimertinib 80 mg/d, or Tarceva 150 mg/d, or Iressa 0.25 g/d.)

Outcome:

Primary outcome was PFS. Secondary outcome include: OS, QoL, tumor size.

Observations and assessments:

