To evaluate the effects of the above treatments on patient safety, tumor size, tumor markers, inflammatory factor levels, quality of life, progression-free survival and overall survival time. General information was collected before and after treatment, and the QoL was assessed on the quality of life questionnaire (QLQ-C30) scale. Chest CT enhancement, brain MRI, liver color Doppler ultrasound, adrenal gland ultrasound, blood test for liver and kidney function, blood and urine routine, tumor markers, tumor necrosis factor, interleukin-6 level were checked every month.

Statistical methods:

The effect of treatment on PFS, OS was analyzed by using Kaplan-Meier probability estimates. Comparison of tumor markers and immune factors was performed using t-test.

Key issues to be addressed:

To explore whether intravenous VitC can prolong resistance time of TKI on lung adenocarcinoma patients with EGFR mutations. To observe whether the combination treatment can benefit NSCLC patients.

Expected results:

Intravenous VitC in combination with TKI can significantly prolong the time of drug resistance, improve the quality of life, and have a positive effect on the prognosis of lung adenocarcinoma patients with EGFR mutations.

Safety measures and emergency plan:

Diarrhea, rash, liver dysfunction and other adverse reactions may occur during the treatment, but the above reactions will be eliminated under the doctor's treatment. If patients experience any discomfort during the study, or if there is a new change in the condition, or any unforeseen circumstances, whether or not related to treatment, patients should promptly notify their doctor, who will make a judgment and medical treatment. If the condition of the disease changes to a certain standard (if the condition progresses), the trial may be terminated earlier after discussion by the research group.

Reference

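### Patients may enter anywhere in the first two months of a new or changed TKI, but no common baseline is defined for tumour size, QoL, tumour markers or inflammatory factors

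*Combined protocol and SAP*

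**What the plan says.** All references are to the combined protocol and SAP.

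- **Inclusion Criteria:** a patient is eligible having "received initial treatment within 2 months, or change medication within 2 months". Time on the current TKI at entry can be anything from 0 to about 2 months, and both newly treated and switched patients are admitted.
- **Method:** in the experimental group "75 patients received a weekly intravenous Vitamin C injection" on top of daily TKI; in the control group "75 patients received only TKI daily". The text states no method of allocation, no stratification and no matching visit for controls.
- **Outcome:** PFS is primary; OS, QoL and tumour size are secondary.
- **Observations and assessments:** "General information was collected before and after treatment"; the same sentence goes on to name QLQ-C30 as the QoL measure. The next sentence lists imaging and laboratory tests and ends "tumor markers, tumor necrosis factor, interleukin-6 level were checked every month". No baseline visit, window or time zero is given.
- **Statistical methods:** tumour markers and immune factors are compared by t-test, without saying whether on change or raw values, or at which visit. No analysis is stated for tumour size or QoL.

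**The concern.** VitC is tested as an addition to an active drug, and patients may join at different points of that drug's response. If the TKI does much of its work in the first weeks, a measurement at entry means something different for a patient in week 1 than for one in week 8: the first still has most of the shrinkage and symptom relief to come, the second has had it.

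The plan does not say what the reference value is. The before-and-after wording is not attached to scans or markers at all. Where it does apply, treatment could mean the TKI, the first infusion or study entry. For a control already on TKI nothing new begins at entry, so no event marks a baseline unless the plan creates one.

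At stake are tumour size, QoL, tumour markers, TNF and IL-6. Their between-arm comparisons could partly reflect how long patients had been on TKI. The start date for PFS is a separate matter and is not part of this point.

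**Working it through.** The plan gives no effect size, SD, alpha or power for these outcomes, so there is no stated figure to reproduce. The sums below are illustrations.

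**Inputs from the document:** 75 patients per arm (Method); entry at 0 to 2 months of TKI (Inclusion Criteria), about 0 to 8.7 weeks.

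**Assumed inputs:** the TKI alone reduces tumour size by 40%, approached exponentially with time constant τ of 2 to 4 weeks; VitC has no effect; other between-patient SD of the change is 20 to 30 points; two-sided alpha is 0.05.

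**Step 1. One patient, different baselines.** Size at TKI week w, relative to TKI start: S(w) = 1 − 0.4 × (1 − exp(−w/τ)). Change over the next 8 weeks: S(w+8)/S(w) − 1. For example, with τ = 2 and w = 4: S(4) = 0.654, S(12) = 0.601, change = 0.601/0.654 − 1 = −8.1%.

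| Baseline at TKI week | τ = 2 | τ = 3 | τ = 4 |
|---|---|---|---|
| 0 | −39.3% | −37.2% | −34.6% |
| 4 | −8.1% | −13.9% | −17.0% |
| 8 | −1.2% | −4.1% | −7.2% |
| Gap, week 0 vs week 4 (points) | 31 | 23 | 18 |
| Gap, week 0 vs week 8 (points) | 38 | 33 | 27 |

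The same tumour shows a change that differs by about 18 to 38 points through baseline timing alone. This is a contrast within one patient, not an arm difference.

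**Step 2. Arm difference with a common anchor and random allocation.** With entry time uniform over 0 to 8.7 weeks, the SD of the 8-week change due to entry time is about 11, 10 and 8 points for τ = 2, 3 and 4. The 95% range of the chance difference between arm means is ±1.96 × SD × √(2/75), or about ±3.5, ±3.1 and ±2.7 points.

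**Step 3. Added noise.** Total SD = √(other SD² + entry-time SD²). With τ = 2 and other SD 20: √(20² + 10.8²) = 22.7, a rise of 14%. With τ = 4 and other SD 30: √(30² + 8.3²) = 31.1, a rise of 4%. The rise is therefore about 4% to 14%.

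**Step 4. What a systematic imbalance would do.** If time on TKI shifted the arm means by b SD with no VitC effect, the false-positive rate would be 1 − Φ(1.96 − b√(75/2)) + Φ(−1.96 − b√(75/2)). This gives 9% for b = 0.1, 23% for b = 0.2 and 45% for b = 0.3. The document has no information on whether such a shift exists.

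**The case against.** Four arguments weigh against a stronger claim.

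1. **Different baselines by arm.** A reader might infer that controls would be measured from a pre-TKI record and VitC patients from just before the first infusion, so that the TKI effect is credited to controls and a VitC effect is hidden or reversed. Nothing in the document says older records would be reused. For QLQ-C30, TNF and IL-6 it is implausible, because a control enrolled while on TKI would normally have no pre-TKI trial value. It could realistically arise only for scans and routine tumour markers. The text leaves it open but does not show it.

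2. **Size.** A reader might take the 27 to 38 point gap as an arm effect, or say that mixed entry times swamp an add-on effect. As an arm difference it would need every control at one extreme and every VitC patient at the other. Steps 2 and 3 show much smaller consequences under a common anchor and random allocation. This stands, with the limit that the document states neither condition. The model also ignores that switched patients may respond differently.

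3. **Progression.** A reader might add that a smaller on-TKI reference makes the same regrowth a larger percentage and so brings progression forward. The document gives no progression criterion. If the reference were the smallest recorded size, it would fall after entry in every case of the assumed curve. This argument is not supported.

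4. **Change scores are assumed.** The plan may intend raw values at a common visit, which use no baseline. In the model, sizes 8 weeks after entry at TKI week 0 and week 8 are then S(8) and S(16): 0.607 and 0.600 for τ = 2, 0.654 and 0.607 for τ = 4. The gap is only 0.7 to 4.7 points of pre-TKI size. This is a fair limit. But the plan does not choose raw values, fixes no visit, and states no analysis for tumour size or QoL.

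What remains is the gap itself: a two-month entry window, no common baseline, and no adjustment for time on TKI.

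**Conclusion.** The point holds as a gap in definition and analysis. Time on TKI at entry varies by up to about 2 months, no shared reference is set, no random allocation is stated, and the only stated comparison for markers is unadjusted. One patient's measured 8-week change could differ by about 18 to 38 points with baseline timing, under the assumed 40% shrinkage and 2 to 4 week time constant. With a common anchor and random allocation, the between-arm consequence shrinks to about ±3 points of chance difference and a 4% to 14% larger SD.

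Bias between arms requires unequal time on TKI or different anchors by arm. Either could occur under the plan as written; neither is shown. A reader should not infer that the plan does favour one arm, or that a VitC effect would be reversed. The outcomes affected are secondary or exploratory, so this should be corrected but does not by itself undermine the trial.

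**What to change.** - **Baseline:** take the first of the planned monthly assessments (scan, QLQ-C30, tumour markers, TNF, IL-6) at allocation in both arms: before the first infusion in the VitC arm and at the matching visit in controls. Allocation is the only anchor every patient can share, since those already on TKI cannot supply new pre-TKI values.
- **Record:** weeks on the current TKI at allocation, and whether it is the initial or a changed TKI.
- **Analysis:** at a stated visit, compare arms on tumour size, QoL, markers and inflammatory factors with a model (ANCOVA or a mixed model) adjusting for the baseline value, weeks on TKI, and initial versus changed TKI, in place of the unadjusted t-test.
- **Pre-TKI scans:** change from a pre-TKI scan, if reported, should be descriptive at most, because patients with such a scan are a subset selected by record availability.

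The cost is protocol wording, a fresh assessment at allocation for some controls, and two covariates besides the baseline value. No dose or treatment rule changes. Adjustment cannot replace random allocation; it deals only with the recorded differences in time on TKI and TKI history.

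### The PFS/OS analysis uses no baseline factor, although EGFR exon and ECOG status must be known at entry; a short prespecified Cox model would add some power if allocation is random and remove measured confounding if it is not

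*Combined protocol and SAP*

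**What the plan says.** The outcome hierarchy in the Outcome section is "Primary outcome was PFS. Secondary outcome include: OS, QoL, tumor size". Statistical methods gives the whole plan for the time-to-event outcomes: "The effect of treatment on PFS, OS was analyzed by using Kaplan-Meier probability estimates". Its only other sentence is "Comparison of tumor markers and immune factors was performed using t-test". Neither names a covariate, a stratification factor, a regression model, a between-arm test or an effect measure for PFS.

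Two patient characteristics are fixed by the Inclusion Criteria: "Primary non-small cell lung cancer (adenocarcinoma) with EGFR mutations on exons 19 and 21" (read here as either exon) and "Eastern Cooperative Oncology Group(ECOG) performance status are 0 to 2". Nobody can be enrolled without both being known.

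Brain-metastasis status is different. It is neither an eligibility item nor a named variable. Brain MRI appears only in Observations and assessments, in the list of monthly tests: "Chest CT enhancement, brain MRI, liver color Doppler ultrasound, adrenal gland ultrasound". No pre-treatment scan is stated.

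On group formation, the Method paragraph says "In experimental group:75 patients received a weekly intravenous Vitamin C injection" and "In the control group:75 patients received only TKI daily". Nothing says how a patient comes to be in one group or the other.

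**The concern.** The plan admits patients of two mutation classes and three performance-status levels, then analyses them as one homogeneous population. If these characteristics predict progression, ignoring them matters in one of two ways, and the missing allocation method leaves open which one applies.

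- **Random allocation.** Gaps between arms are chance and are covered by the standard error. The cost is lost precision: outcome variation that could be explained stays in the comparison.
- **Non-random allocation.** Gaps can be systematic. A fitter vitamin C group would show longer PFS with no treatment effect, and a Kaplan-Meier comparison could not separate the two.

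In both cases the remedy uses data that must exist for exon and ECOG. It is most credible if fixed now, because covariates chosen after the outcomes are seen can be chosen to suit the result.

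**Working it through.** **Inputs from the documents.** There are 75 patients per group. The study period is printed as 12.05.2018 to 31.12.2019. A start on 5 December 2018 gives 391 days, about 12.9 months; a start on 12 May 2018 gives 598 days, about 19.6 months. The plan gives no alpha, power, target effect, control median, event count or prognostic strength, so the 150 patients cannot be re-derived and there is no planned power to reproduce.

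**Assumptions (none from the documents).** Two-sided 5% test, true treatment HR 0.60, exponential PFS with control median 10 or 11 months, 6-month uniform accrual, no dropout. Prevalences: exon 21 45%, ECOG 2 15% or 20%, brain metastases 30%. An unadjusted Cox model stands in for the missing between-arm test.

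**Step 1: chance gaps if allocation is random.** SD of the gap = sqrt(2p(1−p)/75).

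- Exon 21, p = 0.45: SD 0.081, 95% range ±16 points
- Brain metastases, p = 0.30: SD 0.075, ±15 points
- ECOG 2, p = 0.15: SD 0.058, ±11 points

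An exon gap above 10 points occurs in about 22% of trials (0.10/0.081 = 1.23 SD) and above 15 points in about 6.5% (0.15/0.081 = 1.85 SD). A 15-point gap in a factor with prognostic HR 1.6 moves the treatment HR by exp(0.15 × ln 1.6) = 1.07. With 63 events, SE(log HR) is about 2/√63 = 0.25, so this shift is 0.0705/0.25 = 0.28 SE. The 95% interval already spans a factor of exp(1.96 × 0.25) ≈ 1.6 each way.

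**Step 2: power, random allocation.** Unadjusted Cox against Cox adjusted for all three factors, both fitted to the same simulated trials:

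| Window (mean events) | Prognostic HRs: exon / ECOG 2 / brain | Unadjusted | Adjusted | Gain (points) |
|---|---|---|---|---|
| 12.9 months (about 59) | 1.2 / 1.3 / 1.3 | 47.5% | 48.9% | 1.4 |
| | 1.4 / 1.5 / 1.5 | 47.7% | 49.9% | 2.2 |
| | 1.6 / 2.0 / 2.0 | 43.9% | 48.5% | 4.6 |
| 19.6 months (about 84) | 1.2 / 1.3 / 1.3 | 62.7% | 62.4% | −0.3 |
| | 1.4 / 1.5 / 1.5 | 60.4% | 63.1% | 2.7 |
| | 1.6 / 2.0 / 2.0 | 57.3% | 64.8% | 7.5 |
| 12.85 months (about 63) | 1.4 / 1.6 / 1.5 | 50% | 50% | 0 |
| | 1.6 / 2.0 / 1.8 | 48% | 51% | 3 |
| | 1.8 / 2.5 / 2.0 | 45% | 53% | 8 |

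The first six rows use 3,000 trials each (Monte Carlo SE about 0.9 points), control median 11 months and ECOG 2 at 20%. The last three use 500 trials each (about 2 points), median 10 months and ECOG 2 at 15%. The gain is therefore about 0 to 8 points. It comes from three factors; exon and ECOG alone would be expected to give less.

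**Step 3: type I error, random allocation, no true effect.** In the 3,000-trial runs the rejection rate is 4.7–6.0% unadjusted and 5.0–5.8% adjusted, with average HR about 1.00 for both.

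**Step 4: non-random allocation, no true effect.** Let each adverse factor be 10 points rarer in the vitamin C arm. The approximate unadjusted HR is (product of the prognostic HRs)^−0.10:

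- Weak: 2.028^−0.10 = 0.93
- Moderate: 3.15^−0.10 = 0.89
- Strong: 6.4^−0.10 = 0.83

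Simulation over 19.6 months agrees: 0.93, 0.89 and 0.84, with false-positive rates of 6.4%, 7.7% and 13.8%. Adjustment returns the HR to about 1.00 and the rate to 5.2–5.7%. With only exon and ECOG imbalanced, the formula gives 1.56^−0.10 = 0.96, 2.10^−0.10 = 0.93 and 3.20^−0.10 = 0.89.

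**Step 5: can the data carry the model?** For PFS, 59 events over 3 parameters (treatment, exon, ECOG) is about 20 each, and over 4 about 15. Adding TKI drug (2 parameters) and initial v changed TKI (1) to all of these gives 7: about 8 each with 59 events, 12 with 84. For OS, assume median 24 to 36 months and mean follow-up 12.85 − 3 = 9.85 months. At 24 months with no effect, deaths are 150 × (1 − exp(−ln 2 × 9.85/24)) ≈ 37. At 36 months with HR 0.6 they are 75 × 0.173 + 75 × 0.108 ≈ 21. That is 7 to 12 per parameter with 3 parameters, 5 to 9 with 4.

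**The case against.** The strongest reply is that this point is downstream of larger gaps. The plan names no between-arm comparison and no allocation method, so no stated test is losing power, and the covariate list is a sub-clause of repairing that. The ordering is right. But the same sentence that supplies the comparison can carry the covariates, and leaving them out invites a later choice.

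Several stronger readings are tempting, and the documents do not support them:

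- **That all three factors are on file for everyone.** This holds for exon and ECOG. Brain-metastasis status at entry is only a plausible inference from a monthly test list.
- **That chance imbalance invalidates the result.** The documents describe no randomisation, so chance cannot be assumed. Under random allocation, step 3 shows the error rate is sound without adjustment. The 7% shift needs a gap seen in about 6.5% of trials and is small beside the standard error.
- **That an unadjusted HR nearer 1 is an error.** With strong factors and true HR 0.60, the unadjusted HR averages 0.62 against 0.59–0.60 adjusted. That is non-collapsibility: a marginal and a conditional effect differ even under perfect balance.
- **That longer follow-up makes the power loss large.** The stated period ends on 31.12.2019, so gains from 24 months of follow-up lie outside the plan.

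It is also fair that the benefit is modest and rests wholly on assumed inputs.

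**Conclusion.** The omission is real and worth repairing, with a modest expected benefit. The PFS/OS plan uses no baseline factor, while exon and ECOG are necessarily known at entry.

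If allocation is random, adjustment buys about 0 to 8 points of power within the stated period, on a base of roughly 44–63% at an assumed HR of 0.60. It buys next to nothing if the factors are weak, and it corrects no error rate. If allocation is not random, the unadjusted comparison can be biased. In the illustrated three-factor case with no true effect, the HR is 0.93 to 0.84 and the false-positive rate 6.4% to 13.8%. Adjustment deals with measured factors only, so it would not make a non-randomised comparison equivalent to a randomised one.

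A reader should not conclude that the planned analysis is invalid. The documents show only that it leaves known information unused and does not say which of the two situations applies.

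**What to change.** In Statistical methods, state that the between-arm comparison of PFS is a Cox model with treatment, EGFR exon (19 v 21) and ECOG (0–1 v 2), and that Kaplan-Meier curves are descriptive. Add brain metastasis (yes/no) only if a pre-treatment brain MRI is confirmed for all patients. Fix the list before any outcome is seen.

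Consider TKI drug and initial v changed TKI for the same model. Both are visible in the design and equally unused; include them if the PFS event count allows (step 5).

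For OS, use the same model only if the number of deaths supports it, otherwise a reduced covariate set named in advance.

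State how patients are allocated, since that decides whether adjustment is read as a gain in precision or as partial control of confounding.

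The cost is a few sentences of plan text, data already needed for eligibility, and a check on whether a pre-treatment MRI exists. The downsides are that the reported HR becomes a conditional rather than a marginal effect, and that the covariates must be committed to now.

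### QoL and tumour size, two of the three secondary outcomes, have no planned analysis, and the only method stated for continuous measures ignores baseline and names no visit

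*Combined protocol and SAP*

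**What the plan says.** The Objectives section sets out to study the effect of the combination "on the tumor size, QoL, PFS and OS in lung adenocarcinoma patients with EGFR mutation". The Outcome section makes PFS primary and adds: "Secondary outcome include: OS, QoL, tumor size".

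Statistical methods consists of two sentences: "The effect of treatment on PFS, OS was analyzed by using Kaplan-Meier probability estimates", and "Comparison of tumor markers and immune factors was performed using t-test". Neither mentions QoL or tumour size.

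Observations and assessments gives the data collection:

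- **QoL:** "General information was collected before and after treatment, and the QoL was assessed on the quality of life questionnaire (QLQ-C30) scale". The monthly list that follows does not include QoL.
- **Tumour size:** the monthly list opens with "Chest CT enhancement, brain MRI, liver color Doppler ultrasound, adrenal gland ultrasound".
- **Markers:** the same list ends with "tumor markers, tumor necrosis factor, interleukin-6 level were checked every month".

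Under Study design, vitamin C infusions stop once progression is confirmed; no end of TKI treatment is stated for the control arm. Safety measures and emergency plan adds "if the condition progresses), the trial may be terminated earlier after discussion by the research group". That sentence is not limited to one arm, is discretionary and sets no QoL time.

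**The concern.** Two secondary outcomes that are also stated objectives have no analysis. For QoL, the score, visit and method are open. For tumour size, the lesions that count, the summary measure, the visit and the method are open. All of these could be settled after the data are seen. This matters most for QoL, because Expected results already predicts an improvement.

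QoL also has a timing problem. If the before-and-after wording in Observations and assessments is read to cover QLQ-C30, the later value has no calendar time. For a vitamin C patient it would fall at the end of infusions, and so would depend on when that patient progresses. For a control patient the time is undefined. Such values would mix early and late assessments.

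If the marker t-test were simply extended to QoL and tumour size, it would leave the baseline value unused and the visit unnamed, at a real cost in power for a trial of this size.

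**Working it through.** **1. Outcomes against methods**

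| Outcome | Listed as | Instrument or data | Score or measure | Visit | Method |
|---|---|---|---|---|---|
| PFS | primary | – | – | – | Kaplan-Meier |
| OS | secondary | – | – | – | Kaplan-Meier |
| QoL | secondary | QLQ-C30 | none | none fixed | none |
| Tumour size | secondary | monthly imaging | none | none chosen | none |
| Markers | not an outcome | monthly blood tests | – | none chosen | t-test |

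(A dash means not examined for this point.) The plan gives no alpha, power, SD or effect size, so it has no figure to reproduce. What follows is illustrative. Only the 75 per arm comes from the plan (Study design, Method).

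**2. Power with and without baseline**

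Assumptions: two-sided 5%, no dropout, true difference 0.4 SD, arms comparable at baseline on average, baseline-to-follow-up correlation r of 0.5 to 0.7. Power is from the noncentral t distribution, with noncentrality (d / s) × √(n/2), where d = 0.4, n = 75 and s is the analysis SD in units of the outcome SD.

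- Unadjusted two-sample t-test: s = 1. Noncentrality 0.4 × √37.5 = 2.449, 148 df, critical value 1.976. Power **0.682**.
- ANCOVA, r = 0.5: s = √(1 − 0.25) = 0.866. Noncentrality 2.449 / 0.866 = 2.828, 147 df. Power **0.802**.
- ANCOVA, r = 0.7: s = √(1 − 0.49) = 0.714. Noncentrality 2.449 / 0.714 = 3.430, 147 df. Power **0.926**.

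With TKI drug and entry type (initial or changed TKI) added to the model, simulated power was 0.789 to 0.919, with type I error 0.047 to 0.050. The extra covariates therefore cost almost nothing.

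**3. Choosing the visit afterwards**

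The Experimental period runs to 31 December 2019. If the start date means 5 December 2018, the window is 391 days, or 391 / 30.4375 = 12.8 months. With an assumed 6-month accrual the last patient has 12.8 − 6 = 6.8 months, so every patient could have six monthly visits.

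With no true effect, let Z₁ to Z₆ be equally correlated standard normal statistics, positive in favour of vitamin C. The false-benefit rate is P(max Z > 1.96), by simulation:

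| Between-visit correlation | False benefit, best of 6 visits | One fixed visit |
|---|---|---|
| 0.9 | about 5% | 2.5% |
| 0.8 | about 7% | 2.5% |
| 0.5 | about 10% | 2.5% |

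Counting significance in either direction gives 11 to 21% against 5%. The one-direction figures are the relevant ones for a false claim of benefit.

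**The case against.** Several points on the other side stand.

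- **QoL is not without a measure.** QLQ-C30 is named. What is missing is the score, visit and method. Tumour size likewise has a monthly schedule, so its gap is the measurement rule, the choice of visit and the method.
- **The t-test is not an error.** It controls type I error; only power differs. The sentence does not say whether the test is paired or between arms. If it were a between-arm test of change from baseline, the SD would be √(2(1 − r)): power would stay at 0.68 for r = 0.5 but reach 0.88 for r = 0.7, close to ANCOVA's 0.93.
- **Markers are not listed outcomes.** The absence of a log scale is an unspecified choice. Its cost depends on skewness, and the plan gives no marker distribution.

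A reader might also infer three stronger things. The first is that the most favourable visit will be picked. Nothing in the plan says so; the 5 to 10% shows only what the silence permits. The second is that QoL is timed differently in the two arms and is therefore biased. The plan leaves control timing undefined but does not state a different rule. With one rule in both arms and equal PFS, the timing distributions would match and timing alone would favour neither arm. The third is that the trial's main conclusion is at risk. PFS does not depend on this gap.

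Finally, a fixed visit does not remove the effect of progression. Some patients will have progressed or stopped attending by then, so missing values replace variable timing as the issue and must be handled.

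**Conclusion.** The concern holds in a limited form. QoL and tumour size have no planned analysis, and QoL has no fixed assessment time. That is established by reading the plan and rests on no assumption. The t-test on markers, the only comparison stated for continuous measures, is valid but uses neither baseline nor a named visit.

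On the stated assumptions, a baseline-adjusted analysis raises power from 0.68 to between 0.80 and 0.93. A fixed visit holds the false-benefit rate at 2.5%, where free choice among six visits would allow about 5 to 10%. The first figure depends on the assumed 0.4 SD difference and baseline correlation. The second depends on the assumed accrual and between-visit correlation.

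The plan should be changed because the gap affects two of three secondary outcomes and closing it is cheap. It is not a defect in the primary analysis.

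**What to change.** Amend Observations and assessments and Statistical methods as follows.

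1. Give QLQ-C30 at baseline and at the existing monthly assessments in both arms, under the same rule before and after progression.
2. Name QLQ-C30 global health as the QoL score. Define tumour size as percent change from baseline in the summed diameters of lesions measurable on baseline chest CT, and report by arm how many patients have no such lesion.
3. Analyse both by ANCOVA on arm and baseline value, plus TKI drug and entry type, at one pre-stated visit common to both arms (for example month 3), with 95% CIs. Use the same model for the markers in place of the t-test.
4. Report missing values and deaths by arm at that visit. As a sensitivity analysis for missing data, fit a mixed model to the monthly QLQ-C30 values up to that visit.
5. Treat other visits as descriptive and markers as exploratory, using a log scale if they are right-skewed.

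The cost is wording in two sections and one questionnaire at assessments already scheduled. The downsides are extra questionnaires for patients and a tumour-size result limited to those with measurable chest lesions. Two limits remain. The mixed model relies on the observed values to account for missingness. And because patients may enter up to two months after starting or changing TKI, baseline is not always a pre-TKI value; adjusting for entry type covers this only in part.
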